## 1 INTRODUCTION

ALX-0061 (vobarnilizumab) has been developed by the sponsor as a new therapeutic protein neutralizing pro-inflammatory activity in the interleukin-6 (IL-6) pathway. ALX-0061 is a therapeutic protein called nanobody which inhibits the interaction between the IL-6 ligand and the receptor subunit, thereby preventing receptor signaling hence pro-inflammatory activity of IL-6. The investigator's brochure contains more detailed background information. This clinical study (ALX0061-C203) is an open-label extension of Phase IIb studies ALX0061-C201 and ALX0061-C202 and is intended to evaluate the long-term efficacy and safety of ALX-0061 administered subcutaneously (s.c.) to subjects with active rheumatoid arthritis (RA), a chronic systemic inflammatory autoimmune disease.

This statistical analysis plan (SAP) describes the final statistical analysis to be performed for the ALX0061-C203 study. This SAP covers the efficacy, safety, pharmacokinetic, and general characteristics parts of the statistical analysis. It specifies the analysis displays to be presented and describes the methods and procedures in a more elaborated way than in the statistical methods section of the protocol. The statistical analysis will process and present the results following the International Council for Harmonisation (ICH) standards, in particular the ICH-E3, ICH-E6, and ICH-E9 guidelines.

## 2 STUDY OBJECTIVES

The objective of this study is to evaluate the long-term efficacy and safety of ALX-0061 administered s.c. to subjects with active RA.

## 3 STUDY DESIGN

### 3.1 Overall Study Design

This is a multicenter, open-label extension (OLE) phase II study of ALX-0061 administered s.c. in subjects with active RA who have completed the ALX-0061 treatment and assessment period of one of the preceding Phase IIb studies with ALX-0061 (C201 or C202) and who achieved at least 20% improvement in swollen joint count (SJC) and/or tender joint count (TJC) (66/68 counts) compared to baseline at the final visit of the preceding study and for the countries where there was approval for the study.

Eligible subjects will receive ALX-0061 150 mg s.c. injections, beginning at Day 1 (Week 0) of the OLE and every 2 weeks (q2w) thereafter up to and including Week 102. Eligible subjects from study ALX0061-C201 will also continue their methotrexate (MTX) treatment. Subjects will return for 12 ambulatory visits planned at Day 1 (Week 0), and Weeks 4, 8, 12, 24, 36, 48, 60, 72, 84, 96 and 104. Subjects who received study drug up to and including Week 102, should return for the End of Treatment Visit at Week 104 and for the Follow-up Visit 12 weeks after the last study drug administration at Week 102.

In the current OLE study, maintenance of the response will be reassessed at the study visits every 12 weeks from Week 12 until Week 96. Subjects who fail to maintain response and meet efficacy discontinuation criteria (< 20% improvement in both SJC and TJC

compared to baseline of the preceding Phase IIb study) will be discontinued from the study.

The schedule of assessments can be found in [Appendix 1: Schedule of assessments](#).

As this is an OLE study, blinding is not required.

### 3.2 Sample Size

This is an extension study and is not set by statistical power. Subjects who have completed the Week 24 (study ALX0061-C201) or Week 12 (study ALX0061-C202) assessment visit in one of the preceding Phase IIb studies with ALX-0061, and who are qualified for this study per inclusion/exclusion criteria, will be invited to participate in the extension study. Up to a maximum of approximately 501 subjects are planned to participate in this OLE study.

### 3.3 Study Endpoints

The protocol does not define primary or secondary study endpoints. The following endpoints will be analyzed:

#### **Efficacy endpoints:**

- American College of Rheumatology (ACR) ACR20, ACR50, and ACR70 response rate over time (Week 0, Week 12, Week 24, Week 36, Week 48, Week 60, Week 72, Week 84, Week 96 and Week 104).
- Actual values in ACR-N index improvement over time (Week 0, Week 12, Week 24, Week 36, Week 48, Week 60, Week 72, Week 84, Week 96 and Week 104).
- Actual values and change from baseline values in Disease Activity Score using 28 joint counts (DAS28) using CRP and ESR, simplified disease activity index (SDAI) and clinical disease activity index (CDAI) over time (Week 0, Week 12, Week 24, Week 36, Week 48, Week 60, Week 72, Week 84, Week 96 and Week 104).
- Disease activity: response rate of remission and response rate of low disease activity (LDA) based on DAS28(ESR), SDAI, CDAI, Boolean (only remission) over time (Week 0, Week 12, Week 24, Week 36, Week 48, Week 60, Week 72, Week 84, Week 96 and Week 104).
- Disease activity: response rate of DAS28(CRP) < 2.6 and response rate of low disease activity (LDA) based on DAS28(CRP) over time (Week 0, Week 12, Week 24, Week 36, Week 48, Week 60, Week 72, Week 84, Week 96 and Week 104).
- Disease activity: rate of maintained remission at consecutive time points based on DAS28(ESR), SDAI, CDAI, Boolean and rate of maintained LDA at consecutive time points based on DAS28(ESR) over time (Week 0, Week 12, Week 24, Week 36, Week 48, Week 60, Week 72, Week 84, Week 96 and Week 104).
- Disease activity: rate of maintained DAS28(CRP) < 2.6 at consecutive time points and rate of maintained LDA at consecutive time points based on DAS28(CRP) over time (Week 0, Week 12, Week 24, Week 36, Week 48, Week 60, Week 72, Week 84, Week 96 and Week 104).

- European league against rheumatism (EULAR) DAS28 response rate (good, moderate, or no response) over time (Week 0, Week 12, Week 24, Week 36, Week 48, Week 60, Week 72, Week 84, Week 96 and Week 104).
- Actual values and change from baseline values in HAQ-DI over time (Week 0, Week 12, Week 24, Week 36, Week 48, Week 60, Week 72, Week 84, Week 96 and Week 104).
- HAQ-DI response rate (i.e., those who have a clinically meaningful improvement from baseline of  $\geq 0.25$  in HAQ-DI) and HAQ-DI normal physical function response rate (i.e., those who have a score of  $\leq 0.5$ ) over time (Week 0, Week 12, Week 24, Week 36, Week 48, Week 60, Week 72, Week 84, Week 96 and Week 104).
- Actual values and change from baseline values in Physical and mental component scores of SF-36 over time (Week 0, Week 24, Week 48, Week 72 and Week 104).
- Actual values and change from baseline values in FACIT-Fatigue over time (Week 0, Week 24, Week 48, Week 72 and Week 104).
- Actual values and change from baseline values in duration of morning stiffness at Week 0 and Week 104.

**Pharmacokinetic (PK) endpoints:**

- ALX-0061 serum concentration over time (Week 0, Week 12, Week 24, Week 36, Week 48, Week 60, Week 72, Week 84, Week 96 and Week 104).

**Immunogenicity endpoints:**

- Overall subject classification based on ADA/mADA assays results.
- Overall subject classification based on NAb assay results.

**Safety endpoints:**

- Number of events as well as number and percentage of subjects with treatment-emergent Adverse Events (TEAEs), treatment-related AEs, Serious Adverse Events (SAEs), non-serious AEs, treatment-related SAEs, SAEs leading to treatment discontinuation and Adverse Events of Special Interest (AESI), categorized by System Organ Class (SOC) and Preferred Term (PT) and Maximum Severity (where applicable). Note that all adverse events reported in this study are considered treatment-emergent.
- Actual values and change from baseline in clinical laboratory parameters, including blood chemistry, hematology, urinalysis, coagulation and the acute phase proteins (CRP, ESR, and fibrinogen) at Week 0, Week 4, Week 8, Week 12, Week 24, Week 36, Week 48, Week 60, Week 72, Week 84, Week 96, Week 104 and Follow-up (Week 0, Week 24, Week 48, Week 72 and Week 104 only for extended clinical laboratory analyses).
- Shift from baseline in clinical laboratory parameters with normal ranges or CTCAE grades at Week 0, Week 4, Week 8, Week 12, Week 24, Week 36, Week 48, Week 60, Week 72, Week 84, Week 96, Week 104 and Follow-up.
- Actual values and change from baseline values in vital signs measurements at Week 0, Week 4, Week 8, Week 12, Week 24, Week 36, Week 48, Week 60, Week 72, Week 84, Week 96, Week 104 and Follow-up.
- Physical examination abnormal findings at Week 0, Week 12, Week 24, Week 36, Week 48, Week 60, Week 72, Week 84, Week 96, Week 104 and Follow-up.

## 4 GENERAL ASPECTS FOR STATISTICAL ANALYSIS

### 4.1 Analysis Populations

The following populations will be considered for analysis:

#### 4.1.1 *All screened population*

The all screened population includes all subjects who signed an informed consent for participation in the ALX0061-C203 study.

#### 4.1.2 *Intent-to-observe (ITO) population*

The ITO population includes all subjects who enrolled in study ALX0061-C203 and is thus equal to the all screened population. General characteristics and efficacy will be analyzed on the ITO population.

#### 4.1.3 *Safety population*

The safety population includes all subjects who received at least 1 administration of study drug, as treated. The safety population will be used for the analysis of exposure and safety data.

#### 4.1.4 *PK population*

The PK population is a subset of the safety population and consists of all subjects who received at least 1 administration of ALX-0061 and for whom at least one ALX-0061 serum concentration has been determined.

The PK population will be used for the analysis of ALX-0061 serum concentrations.

### 4.2 Key Definitions and Labels

#### 4.2.1 *Definition of baseline and change from baseline*

The baseline value will be the baseline value of the parent study.

The absolute change from baseline will be calculated for all post-baseline time points as:  
Change from baseline at time point t = value at time point t – baseline value

For selected efficacy endpoints, the percentage change from baseline will be calculated for all post-baseline time points as: Percentage change from baseline at time point t =  $100 * (value at time point t - baseline value) / baseline value$ . As percentage change can not be calculated for subjects with a baseline value of 0, these subjects will not be included for the corresponding summary analysis (if planned) and the respective column(s) will be kept blank for the corresponding listing.

For the changes from baseline, only subjects with both a baseline value and a value at the post-baseline time point will be included.

Wherever in the document 'change from baseline' is mentioned, it concerns the absolute change from baseline.

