All values will be compared to their matching normal ranges (low, normal, high). For both values and normal ranges the SI units will be considered to determine abnormalities. Additionally, for key hematology and biochemistry parameters, toxicities will be derived according to the common terminology criteria for adverse events (CTCAE, see appendix 16.2) grading, version 4.03 (ALT, AST, total bilirubin, gamma-glutamyltransferase, leukocytes, neutrophils, thrombocytes, fibrinogen and cholesterol). Details for derivation of classification based on normal ranges of laboratory parameters can be found in section 12.4.2.

Cross-tabulations per lab test category (hematology, biochemistry, acute phase proteins, urinalysis, coagulation), lab test and time point will show the shift at each post-baseline time point versus the baseline.

The following types of cross-tabulations will be prepared:

- for all tests with normal ranges: shift in abnormality (L/N/H)
- for ALT, AST, total bilirubin, GGT, leukocytes, neutrophils, thrombocytes, fibrinogen and lipids test results only: shift in CTCAE toxicity grades (grade 1 to 4)

Longitudinal box plots will be prepared for the following variables: neutrophils, platelets, ALT, AST and LDL/HDL ratio.

A detailed list of tables, figures and listings can be found in section 13.4, section 14 and section 15.4, respectively.

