#### 12.4.2 Laboratory

Values will be scored as abnormally low (L), normal (N) or abnormally high (H). A value is classified as abnormally low when the value < lower limit of the normal range. A value is classified as abnormally high when the value > upper limit of the normal range. Tests without normal ranges will not be scored.

An original value like “<X” where X equals the lower limit of the normal range will be classified as abnormally low (L). An original value like “>X” where X equals the upper limit of the normal range will be classified as abnormally high (H).

Urinalysis tests for which a normal range is available, will also be categorized as L, N, or H. If there is doubt on whether the result is within normal range or not, the worst-case will be taken. E.g., when the test result equals “4 to 6” and the normal range is 0-5, then the test result will be classified as abnormally high (H) if it is a post-baseline visit, and will be classified as normal (N) if it is a baseline visit. In such cases, the original urinalysis test result will not be used for the tables, but will only be listed. Urinalysis tests for which no normal range is available, will be tabulated separately as categorical data.

All nonmissing post-baseline values (including unscheduled measurements and follow-up measurements) will be used to derive the following worst-case abnormalities for each parameter:

- H = abnormally high: at least one postdose measurement is above the normal range, and there are no values below the normal range.
- L = abnormally low: at least one postdose measurement is below the normal range, and there are no values above the normal range.
- H+L = abnormally high and low: at least one postdose measurement is above the normal range, and at least one other postdose measurement is below the normal range.
- N = normal: all postdose measurements are within normal limits.

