**Table 14.3.2.3: Laboratory data: Cross-tabulation of the abnormalities per time point**

Cross-tabulation per lab test category (hematology, biochemistry, acute phase proteins, urinalysis, coagulation), lab test and time point.

Population: safety population.

**Table 14.3.2.4: Laboratory data: Cross-tabulation of the CTCAE toxicity per time point for key hematology and biochemistry parameters**

Cross-tabulation per lab test category, lab test and time point.

Population: safety population.

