**Table 14.3.2.5: Laboratory data: Cross-tabulation of the worst-case abnormalities**

Cross-tabulation per lab test category (hematology, biochemistry, acute phase proteins, urinalysis, coagulation) and lab test.

Population: safety population.

**Table 14.3.2.6: Laboratory data: Cross-tabulation of the worst-case CTCAE toxicity for key hematology and biochemistry parameters**

Cross-tabulation per lab category and lab test.

Population: safety population.

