**Listing 16.2.8.2: Laboratory data: Abnormalities**

Listing similar to 16.2.8.1, but only consisting of data scored as out-of-normal-range or clinically significant, plus also the baseline reference time point.

Population: safety population.

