Definition: A finding based on laboratory test results that indicate an increase in levels of creatine phosphokinase in a blood specimen.					

Investigations						
Adverse Event	Grade					
	1	2	3	4	5	
Creatinine Increased	>1 - 1.5 x baseline; >ULN - 1.5 x ULN	>1.5 - 3.0 x baseline; >1.5 - 3.0 x ULN	>3.0 baseline; >3.0 - 6.0 x ULN	>6.0 x ULN	-	
Definition: A finding based on laboratory test results that indicate increased levels of creatinine in a biological specimen.						
Ejection fraction decreased	-	Resting ejection fraction (EF) 50 - 40%; 10 - 19% drop from baseline	Resting ejection fraction (EF) 39 - 20%; >20% drop from baseline	Resting ejection fraction (EF) <20%	-	
Definition: The percentage computed when the amount of blood ejected during a ventricular contraction of the heart is compared to the amount that was present prior to the contraction.						
Electrocardiogram QT corrected interval prolonged	QTc 450 - 480 ms	QTc 481 - 500 ms	QTc >= 501 ms on at least two separate ECGs	QTc >= 501 or >60 ms change from baseline and Torsade de pointes or polymorphic ventricular tachycardia or signs/symptoms of serious arrhythmia	-	
Definition: A finding of a cardiac dysrhythmia characterized by an abnormally long corrected QT interval.						
Fibrinogen decreased	<1.0 - 0.75 x LLN or <25% decrease from baseline	<0.75 - 0.5 x LLN or 25 - <50% decrease from baseline	<0.5 - 0.25 x LLN or 50 - <75% decrease from baseline	<0.25 x LLN or 75% decrease from baseline or absolute value <50 mg/dL	-	
Definition: A finding based on laboratory test results that indicate a decrease in levels of fibrinogen in a blood specimen.						
Forced expiratory volume decreased	FEV1% (percentages of observed FEV1 and FVC related to their respective predicted values) 99 - 70% predicted	FEV1 60 - 69%	50 - 59%	<= 49%	-	
Definition: A finding based on test results that indicate a relative decrease in the fraction of the forced vital capacity that is exhaled in a specific number of seconds.						
GGT Increased	>ULN - 2.5 x ULN	>2.5 - 5.0 x ULN	>5.0 - 20.0 x ULN	>20.0 x ULN	-	
Definition: A finding based on laboratory test results that indicate higher than normal levels of the enzyme gamma-glutamyltransferase in the blood specimen. GGT (gamma-glutamyltransferase) catalyzes the transfer of a gamma glutamyl group from a gamma glutamyl peptide to another peptide, amino acids or water.						

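### In the C201 PBO + MTX arm, the laboratory shift and worst-case tables mix placebo-period with on-drug change, because their reference is the parent-study baseline and not the last value before first drug

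*SAP*

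**What the plan says.** SAP 4.2.1 defines the reference without exception: "The baseline value will be the baseline value of the parent study". Protocol 3.6.6 says the same for safety, so this is a deliberate choice.

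SAP 7.2 states that the laboratory cross-tabulations "will show the shift at each post-baseline time point versus the baseline". They appear in SAP 13.4 as Table 14.3.2.3, "Laboratory data: Cross-tabulation of the abnormalities per time point", and Table 14.3.2.5, "Laboratory data: Cross-tabulation of the worst-case abnormalities". Tables 14.3.2.4 and 14.3.2.6 are the CTCAE counterparts.

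For the worst case, SAP 12.4.2 says: "All nonmissing post-baseline values (including unscheduled measurements and follow-up measurements) will be used to derive the following worst-case abnormalities for each parameter". Its category definitions use another term; High, for example, requires that "at least one postdose measurement is above the normal range, and there are no values below the normal range".

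The C201 PBO + MTX group is the only placebo label in SAP 4.2.2. SAP 3.3 lists Week 0 among the shift time points. By footnote B of SAP Appendix 1, the Week 0 laboratory value of C201 subjects is their C201 Week 22 sample.

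Nine tests are graded by CTCAE (SAP 7.2). In SAP Appendix 3, fibrinogen is the only one of the nine whose grade refers to baseline; Grade 2 is "<0.75 - 0.5 x LLN or 25 - <50% decrease from baseline".

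**The concern.** Protocol 1.2.5 discusses falls in neutrophils, platelets and fibrinogen, and rises in transaminases and lipids, as effects of IL-6 pathway inhibition. In C203 only the former placebo arm goes from no ALX-0061 to ALX-0061. For that arm a natural question is how many subjects were normal at the last sample before first drug and abnormal afterwards.

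No planned table crosses this arm's on-drug values with its Week 0 value. An abnormality that arose on placebo + MTX and persisted is counted as a shift at each later visit. A subject who was abnormal at parent baseline, normal at Week 0 and abnormal again on drug appears as unchanged. The worst-case tables have no time dimension, so the reader lacks even a Week 0 row for comparison. If the Week 0 sample counts as post-baseline, an abnormality seen only before first drug can be this arm's worst value. The fibrinogen grade takes its percentage fall from the same distant reference.

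**Working it through.** The documents give no arm size, abnormality rate or laboratory distribution, so there is no figure of the plan's own to reproduce. Steps 1 and 3 use document values only. The counts, rates and changes in the other steps are assumed.

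**1. Timing.** C201 lasts 24 weeks: parent baseline to first ALX-0061 dose is 24 × 7 = 168 days. The Week 22 sample precedes that dose by (24 − 22) × 7 = 14 days.

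**2. What the Week 0 row gives.** Take N subjects normal at parent baseline, a of them abnormal at Week 0 and b abnormal at a later visit. The number normal at Week 0 and abnormal later lies between max(0, b − a) and min(b, N − a). No distribution is needed.

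| N | a | b | Newly abnormal since Week 0 |
|---|---|---|---|
| 60 | 6 | 6 | 0 to 6 |
| 100 | 2 | 15 | 13 to 15 |
| 100 | 5 | 15 | 10 to 15 |
| 100 | 10 | 15 | 5 to 15 |
| 100 | 20 | 15 | 0 to 15 |

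The row is informative when few are abnormal at Week 0 and uninformative when a is as large as b.

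**3. What the entry limits already settle.** Exclusion 12 (protocol 3.2.2) applies to the same Week 22 sample.

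| Test | Excluded at entry | CTCAE Grade 2 begins |
|---|---|---|
| ALT, AST | ≥ 2 × ULN | > 3 × ULN |
| Neutrophils (10⁹/L) | < 1.5 | < 1.5 |
| Platelets (10⁹/L) | ≤ 75 | < 75 |

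Apart from eligibility deviations, every on-drug value of Grade 2 or higher in these tests is new since that sample, whatever the reference. Only Low/Normal/High and Grade 1 remain ambiguous. Fibrinogen, cholesterol, GGT, bilirubin and leukocytes have no numerical entry limit, only the investigator's judgement (12f), so all their grades remain open.

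**4. Worst case with Week 0 counted.** Among subjects normal at parent baseline, let a fraction q be abnormal at Week 0 and resolve on drug, and let 5% of the others become abnormal on drug. The table shows q + (1 − q) × 0.05; the on-drug part is (1 − q) × 0.05. For q = 2%, 5% and 10% this is 6.9 against 4.9%, 9.8 against 4.8%, and 14.5 against 4.5%. Full resolution is the extreme case; step 6 gives a milder one.

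**5. Fibrinogen.** With a placebo-period fall x and an on-drug fall e, the graded fall is 1 − (1 − x)(1 − e). Grading by percentage only:
- x = 10%, e = 20%: 1 − 0.90 × 0.80 = 28%, Grade 2; from the pre-dose value 20%, Grade 1.
- x = −10% (a rise), e = 30%: 1 − 1.10 × 0.70 = 23%, Grade 1; from the pre-dose value 30%, Grade 2.

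The error can go either way. Now assume a mean on-drug fall of 30% (log SD 0.20), a placebo-period log SD of 0.15 or 0.20, and correlation −0.5 between the two changes because they share the Week 0 value. Grade 3 or higher is then 4.6% from the pre-dose value. From parent baseline it is 3.1–4.6% with no mean placebo change, 10.0–12.4% after a 10% fall and 0.8–1.5% after a 10% rise.

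**6. ALT illustration.** Simulated log(ALT/ULN), centred on 0.5 × ULN, SD 0.45. Correlation is 0.7 among Week 0 and 12 later samples, and 0.5 or 0.7 with parent baseline. Placebo-period drift is 0, 0.1 or 0.2 on the log scale, with no drug effect and Week 0 below 2 × ULN. Rates are shares of all subjects in the arm.
- Normal to High from parent baseline is 3.6–10.7% at both Week 0 and Week 12, so group rates agree.
- Of the Week 12 shifts, 28–45% were already High at Week 0.
- Of those Normal at Week 0 and High at Week 12, 13–28% appear as High to High.
- Worst-case Normal to High is 17.9–35.4% from parent baseline and 17.9–28.1% from the pre-dose value. With no drift and correlation 0.7 throughout it is 17.9 against 18.0%.
- Counting Week 0 in the worst case adds 0.6–0.9 percentage points.

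**The case against.** The parent-study baseline is prespecified, was clarified in protocol version 3.0, and is right for every arm already on ALX-0061. The study is descriptive and its objective is long-term safety. The effect of starting drug against placebo belongs to C201, and an uncontrolled shift from one variable Week 22 sample would not prove causation. All of this stands, and it is why the main tables should not change.

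Much is also covered elsewhere. Week 0 rows let group means and changes be separated. Figure 14.3.1.1 gives box plots over time by treatment group for neutrophils, platelets, ALT, AST and the LDL/HDL ratio. Clinically significant laboratory findings become adverse events (protocol 3.4.4.2), and the main AE tables count only events starting after the first C203 dose (SAP 7.1). Listing 16.2.8.1 holds every raw value with its L/H flag, so the missing cross-tabulation can be rebuilt by hand. The shorter abnormality listing does not help: it is described as "only consisting of data scored as out-of-normal-range or clinically significant, plus also the baseline reference time point", so a normal Week 0 value is absent and looks the same as a missing one.

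The larger rate differences in steps 5 and 6 come from assumed placebo-period drifts that the documents do not report. A fall in fibrinogen is also an expected pharmacological effect. And the category definitions in SAP 12.4.2 already say postdose, which can be read as excluding Week 0.

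A reader might infer that the tables cannot show anyone moving from normal before drug to abnormal after it. That goes too far: for this arm the parent baseline is itself before first ALX-0061, so a shift from it is such a move. What is missing is the shift from the last pre-drug value.

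**Conclusion.** The point holds as a minor one. As written, the rule gives the C201 PBO + MTX arm a laboratory reference that mixes nominally 24 weeks of placebo-period change with on-drug change in four tables, and SAP 12.4.2 allows a pre-drug sample into its worst case. For ALT, AST, neutrophils and platelets the ambiguity stops at Low/Normal/High and Grade 1. For the five graded tests without an entry limit it reaches all grades, and the fibrinogen grade itself changes with the reference.

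The real size cannot be computed from the documents. Only the bound in step 2 is free of distributional assumptions, and its counts are illustrative. With no mean placebo change the simulated group rates differ little, and the main loss is which subjects are newly abnormal. The documents do not support reading this as a concealed Grade 2 or higher signal in transaminases, neutrophils or platelets, or as a fault in the baseline for the other arms.

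**What to change.** Keep the parent-study baseline in all main tables, as protocol 3.6.6 requires.

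- In SAP 7.2 and 13.4, add supplementary versions of Tables 14.3.2.3 to 14.3.2.6 for the C201 PBO + MTX arm only. The reference is the last value before the first C203 dose: the C201 Week 22 sample, or a later pre-dose test if there is one. Use it for the fibrinogen grade as well.
- In SAP 12.4.2, state that only values after the first C203 dose count towards this arm's worst case.
- Record the addition in SAP 11.

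The cost is four one-arm tables from data already collected, plus one clause. The arm then has two reference points, which a footnote must explain. The supplementary tables will not sum to the pooled columns, and a single Week 22 value is itself variable. Supplementary versions of the descriptive laboratory and vital-sign tables (14.3.2.1 and 14.3.3.1) are not needed.
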